#### *Secondary hypotheses:*

H2a Compared to usual care, implementation of the IP will result in significant improvement in service delivery at 12 and 26 weeks post injury as related to increased occasions of service

H2b Compared to usual care, implementation of the IP will result in significant improvement in service delivery at 12 and 26 weeks post injury as related to increased compliance with minimum process of care indicators

H3 Compared to usual care, implementation of the IP will result in significant improvement in neurological disability (Modified Rankin Scale) and independence (Functional Independence Measure) at 12 and 26 weeks post injury

H4 Compared to usual care, implementation of the IP will result in significantly reduced carer burden (Modified Caregiver Strain Index) and less brain injury survivor anxiety and depression (Hospital Anxiety and Depression Scale) at 12 and 26 weeks post injury

H5 The culturally sensitive IP will be more cost-effective (additional benefits gained will justify additional costs for delivering the intervention; may lead to potential cost-offsets from less severe disease) than usual care at 12 and 26 weeks post injury.

H6 The IP will be acceptable to health professionals and Aboriginal participants and their families, and the role of the Aboriginal Brain Injury Coordinator a feasible one.

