#### **16.4.2 Secondary outcomes analyses**

A mixed effects logistic regression model will be used to assess the impact of the intervention on the odds of achievement of the minimum processes of care [H2a]. The outcome variable will be a binary variable: minimum processes of care received by patient in the first 26 weeks post brain injury versus minimum processes of care not received by patient in the first 26 weeks post brain injury. Time will be included as a fixed effect in the model to control for the effects of secular trends. Site will be included as a random effect in the model.

A linear mixed effects regression model will be used to assess the impact of the intervention on the occasions of service [H2b]. The outcome variable will be the count of the occasions of service in the first six months post brain injury. Type and severity of the brain injury will be controlled for in the model. Time will be included as a fixed effect in the model to control for the effects of secular trends. Site will be included as a random effect in the model.

To examine the secondary outcomes of effects of the intervention on stroke/TBI disability and independence after injury [H3], the mRS score will be dichotomised into good outcome (mRS 0-2) and poor outcome (mRS 3-6). A logistic generalized linear mixed model will be developed to assess the impact

of the intervention on mRS at baseline, 12 and 26 weeks after injury. Within-cluster effects will be controlled for in the model and deviations from the protocol caused by changes in care site will be included as random effects.

A longitudinal linear mixed model will be used to assess the impact of the intervention on carer burden [H4]. The outcome variable will be the Modified Caregiver Strain Index at 12 and 26 weeks post brain injury. Type and severity of the brain injury will be controlled for in the model. Time period will be included as a fixed effect in the model to control for the effects of secular trends. Site will be included as a random effect in the model.

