A longitudinal linear mixed model will be used to assess the impact of the intervention on anxiety and depression [H4]. The outcome variable will be the Hospital Anxiety and Depression Scale at 12 and 26 weeks post brain injury. Type and severity of the brain injury will be controlled for in the model. Time period will be included as a fixed effect in the model to control for the effects of secular trends. Site will be included as a random effect in the model.

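### The H3 disability model names no calendar-period effect, unlike every other efficacy model, and lists baseline mRS among its outcomes

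*Protocol*

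**What the plan says.** In the protocol, section 16.4.2, the H3 paragraph dichotomises mRS at 0-2 against 3-6 and fits a logistic mixed model, worded as the effect "of the intervention on mRS at baseline, 12 and 26 weeks after injury. Within-cluster effects will be controlled for in the model". The only further term listed is a random effect for protocol deviations due to changes of care site. Neither calendar time nor a participant effect is named.

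The other efficacy models do address calendar time:
- Primary model (section 16.4.1): a mixed linear model stated to control for secular trends.
- Both H2 models (process of care, occasions of service): "Time will be included as a fixed effect in the model to control for the effects of secular trends".
- Both H4 models (carer burden, anxiety and depression): "Time period will be included as a fixed effect in the model to control for the effects of secular trends".

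Hypothesis H3 itself (synopsis, sections 4.2 and 16.1) sets the time points for disability and "independence (Functional Independence Measure) at 12 and 26 weeks post injury". Baseline is not among them.

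**The concern.** In a stepped wedge, each cluster passes from control to intervention once and never back, so all its control participants are recruited before its intervention participants. A model that compares conditions within clusters without a period effect cannot tell the intervention from whatever else changed over those years. Drift towards better outcomes would look like benefit. Drift towards worse outcomes would hide a benefit or look like harm. The protocol expects such change: section 5 anticipates changes of staff and of local service organisation, and section 11.1.1 refers to COVID-19.

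The visit schedule does not stand in for the missing term. Baseline, week 12 and week 26 measure time since injury, not calendar time.

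The second, lesser issue is the baseline visit. If one intervention effect is estimated over all three visits, it averages in a visit to which the hypothesis does not apply.

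**Working it through.** **1. The plan's own figures.** The protocol gives no drift, effect size or power for H3. Section 16.3 covers the primary outcome only: 15/25 = 0.6; 45 per arm in a two-sided t-test gives power 80.4%, so 90 in total; and 13 x 4 pairs x 6 periods = 312. Both totals reproduce, taking the cluster as the pair of sites (section 5). The same layout is used below.

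**2. Calendar gap between conditions.** Inputs from section 5: four pairs, 26-week steps, and 52 weeks after the last step, hence six periods, numbered 0 to 5. For a pair with c control periods, the mean period is (c-1)/2 under control and (c+5)/2 under intervention.

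| c | Control mean | Intervention mean | Gap |
|---|---|---|---|
| 1 | 0.0 | 3.0 | 3.0 |
| 2 | 0.5 | 3.5 | 3.0 |
| 3 | 1.0 | 4.0 | 3.0 |
| 4 | 1.5 | 4.5 | 3.0 |

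The gap is 3 x 26 = 78 weeks (18 months) in every cluster, so adjusting for cluster does not remove it. Pooling all cells, control averages 10/10 = 1.00 and intervention 50/14 = 3.57, a gap of 2.57. A random cluster effect lies between 2.57 and 3.0.

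**3. Conditional scale.** A drift odds ratio of r per period appears as r cubed: 1.05 gives 1.16, 1.10 gives 1.33 and 1.20 gives 1.73.

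**4. Simulation.** 312 participants at 8 sites, three visits, no true intervention effect. Assumed: site ICC 0.08 and participant SD 2 on the logit scale. Fitted: logistic regression with site and visit as fixed effects and participant-robust standard errors, 600 runs per row (Monte Carlo error near 5%: sqrt(0.05 x 0.95/600) = 0.9 points). The odds ratios are marginal, hence smaller than in step 3.

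| Drift OR per period | OR, no period term | False positives | OR, with period | False positives |
|---|---|---|---|---|
| 1.00 | 1.01 | 6.0% | 0.99 | 5.7% |
| 1.05 | 1.08 | 7.0% | 0.98 | 6.5% |
| 1.10 | 1.20 | 16.0% | 0.99 | 6.2% |
| 1.20 | 1.42 | 43.8% | 1.01 | 4.5% |

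**5. Baseline as an outcome.** Assume a conditional odds ratio of 2 at weeks 12 and 26, none at baseline, and no drift. One effect over three visits gives a marginal odds ratio of 1.36, against 1.54 at week 26 alone. On the log scale, 0.307/0.432 = 0.71, so roughly 30% of the effect is lost. Rejection rates were close (35% and 37%), so the harm in this scenario is to the estimate rather than to power.

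**6. Price of the period term.** No variance is given for H3, so the linear primary outcome serves as an analogue: SD 25, ICC 0.08, 4 clusters, 13 per cluster-period. The standard error is 4.99 with period effects and 2.94 without, a ratio of 1.70.

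**The case against.** The strongest reply is that this is a drafting gap in one secondary model. The primary model controls for secular trend, the missing sentence appears elsewhere in the same section, and an analysis plan that is not shown may supply it. That stands as a reason for moderate severity. It does not remove the point: the protocol settles calendar time for five models and lists the terms of the sixth without it.

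On baseline, the synopsis does list mRS at baseline, 12 and 26 weeks as a secondary measure, and keeping baseline in the response is legitimate with visit-specific intervention effects. Dilution follows only if one common effect is fitted, and the protocol states neither choice. This is therefore a matter to reconcile, not a demonstrated error.

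A reader might infer more than the protocol supports:
- **H4 standard errors too small.** Both H4 paragraphs name one random effect ("Site will be included as a random effect in the model") for two visits per person. But they call the models longitudinal mixed models, which ordinarily implies within-person correlation, and its form is commonly left to the analysis plan. At most, the participant effect could be named. Nor is H4 open to the drift problem, since it has a period effect.
- **Dichotomised mRS.** A pre-specified split is a defensible choice. An ordinal model would bring an assumption of its own.
- **Care-site changes as post-allocation adjustment.** They enter as random effects, not covariates, and sections 6 and 11.1.2 anticipate transfers.
- **FIM.** Section 16.4.2 describes no FIM model, so there is none to fault here.

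**Conclusion.** The point holds for H3 alone. As written, the disability model confounds the intervention with calendar time, and inconsistently with the rest of the plan. The threefold loading is arithmetic from the six-period layout, with even recruitment across periods. The size of any false effect is not known: it rests on an assumed drift, and on the scale. A drift odds ratio of 1.10 per period shows as about 1.20 marginally and 1.33 conditionally, so neither should be quoted as the expected bias. With little or no drift, the omission does little harm.

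The listing of baseline mRS as an outcome conflicts with the time points of H3 and needs a stated reason or a correction. The outcome is secondary and the primary analysis is unaffected, so this should be fixed but does not threaten the trial's main result.

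**What to change.** In the H3 paragraph of section 16.4.2:
- Add calendar period as a fixed effect, using the sentence already written for the H2 and H4 models.
- Take mRS at weeks 12 and 26 as the outcomes, with participant and site random effects and baseline mRS as a covariate. Alternatively, keep baseline in the response and add visit-by-intervention terms, so that the week 12 and week 26 effects are estimated separately.
- Justify the choice. Section 10.2.1 allows baseline up to 42 days after injury, possibly after contact with the intervention; adjusting for a baseline already affected could remove part of the effect.

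The cost is a few sentences and no new data. The H3 confidence interval will be wider, by a factor of about 1.7 in the linear analogue, but the narrower interval without period effects is valid only if there is no drift.

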Healthcare workers reported similar issues, but from the service provider perspective. General Practitioners, Speech Pathologists and Aboriginal Health Workers all commented on a lack of a) coordination and communication between health service providers, b) accessible information regarding brain injury rehabilitation and c) culturally appropriate therapy resources. Many felt ill-equipped to work with Aboriginal families due to lack of confidence in what was culturally appropriate to discuss, how to structure family meetings, and knowledge of linguistic and cultural customs in general. Many felt rehabilitation and services were not always wanted by Aboriginal brain injury survivors.

The current project will translate the findings of both previous studies across WA and will test the impact of a research-informed *culturally secure* intervention model for Aboriginal people with brain injury in WA. This will occur in partnership with WA Department of Health services and Aboriginal Community Controlled Health Services, as well as national policy-makers. The project addresses the systemic challenges identified in our research using existing resources where possible, and developing a site and service specific sustainable evidence-based approach. Due to the chronic nature of consequences of brain injury, the proposed intervention package follows a Chronic Care Model (CCM) demonstrated to be successful in the management of other chronic conditions, incorporating specific components related to brain injury. This clinically oriented model aims to reshape the ambulatory care system into one characterised by multi-disciplinary team involvement, continuity and integration of care, proactivity, flexibility, and self-management, all aimed at preventing complications and improving quality of life. This project will also increase workforce capacity by employing Aboriginal Community Nurses/Health Workers as Aboriginal Brain Injury Coordinators in the management of brain injury survivors. It will facilitate a more integrated, collaborative and culturally secure response to brain injury between hospital, rehabilitation, and community services (both ‘mainstream’ and Aboriginal community controlled). This model can then be applied nationally. The project is aligned with Priority 4 of the WA Health Strategic Intent 2015 – 2020^23 and adheres closely to the NHMRC Roadmap II.

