**Figure 1: Stepped wedge design**

Jan-Jun'17	Jul-Dec'17	Jan-Jun'18	Jul-Dec'18	Jan-Jun'19	Jul-Dec'19	Jan-Jun'20	Jul'20-Jul'21
Project	Sites 7&8	Sites 7&8	Sites 7&8	Sites 7&8	Sites 7&8	Sites 7&8	Analysis Feedback & Write up
Set-up including ethics, staff recruitment	Sites 5&6	Sites 5&6	Sites 5&6	Sites 5&6	Sites 5&6	Sites 5&6	
	Sites 3&4	Sites 3&4	Sites 3&4	Sites 3&4	Sites 3&4	Sites 3&4	
	Sites 1&2	Sites 1&2	Sites 1&2	Sites 1&2	Sites 1&2	Sites 1&2	

\*Dark Shaded area = baseline control observational data collection; Light Shaded area = intervention underway

Due to the complex nature of the intervention i.e. multiple components, broad site base (including very different local contexts across sites), potential contamination across sites due to movement of some patients from rural to metropolitan hospitals, and potential clinical changes throughout the intervention period (e.g., changes of staff, changes in local organisation of services), a process evaluation will be undertaken alongside measurement and analysis of the intervention and primary outcomes as per the TIDieR checklist.

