## **6 Study Setting**

Eight acute hospital sites across Western Australia will participate in the study. These include four Perth metropolitan sites (Sir Charles Gairdner Hospital, Royal Perth-Bentley Hospital, Fiona Stanley-Fremantle Hospital, St John of God Midland Hospital) and four regional sites (Broome Hospital, Kalgoorlie Hospital, Geraldton Hospital and Hedland Health Campus, Port Hedland). Transfer across hospitals within WA is anticipated, and ‘step-down’ rehabilitation sites will be involved (ethics approval obtained) for participant follow-up but not recruitment.

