## **8 Site Randomisation**

Sites will be randomised at the beginning of the project to determine the sequencing of the introduction of the intervention period.

It is anticipated that numbers of participants recruited in metropolitan sites may be higher than in regional sites due to potential transfer of patients to tertiary metropolitan hospitals for early treatment post injury. In order to minimise potential differences in participant numbers across steps in the wedge, one metropolitan and one regional site (cluster) will be paired prior to randomisation, then these pairs of sites will be randomised. Sites will be assigned to a particular intervention commencement time through the use of computer-generated sequence of random numbers. The process will allocate sites to one of four commencement periods (see Figure 1).

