### **16.4 Statistical Analyses**

The primary analysis will be performed on an intention to treat basis with each participant allocated to the site at which he/she was originally recruited.

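### The H3 (mRS) model includes a term for changes of care site, which come after allocation, so it can miss the total effect of the package

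*Protocol*

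**What the plan says.** Section 16.4.2 dichotomises mRS into 0-2 against 3-6 and fits a logistic mixed model over baseline, 12 and 26 weeks. It controls for within-cluster effects and adds that "deviations from the protocol caused by changes in care site will be included as random effects". It does not say what these random effects are: a yes/no deviation indicator, an effect of the final care site, or a multiple-membership structure.

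The neighbouring models differ. Those for minimum processes of care, occasions of service, carer strain and HADS use site as a random effect and time as a fixed effect. All of these except the processes-of-care model also control for type and severity of injury. The H3 text states no severity adjustment.

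Three other places bear on the point:

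- Allocation: section 8 says "Sites will be randomised at the beginning of the project to determine the sequencing of the introduction of the intervention period".
- Analysis set: section 16.4 says "The primary analysis will be performed on an intention to treat basis with each participant allocated to the site at which he/she was originally recruited".
- Movement of patients: section 6 says "Transfer across hospitals within WA is anticipated", and section 5 names "potential contamination across sites due to movement of some patients from rural to metropolitan hospitals" among the reasons for a process evaluation. Section 11.1.2 makes coordinator contact after a transfer depend on whether the recruiting site has the service, and has departures from the prescribed protocols reported as deviations.

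**The concern.** A change of care site, and any deviation it causes, comes after the sequence of sites has been randomised. It is also something the package could change. Section 3 says of the project: "It will facilitate a more integrated, collaborative and culturally secure response to brain injury between hospital, rehabilitation, and community services". The coordinator's role is liaison and advocacy, and transferred participants are handled according to the recruiting site's phase. What happens at a change of site, and what counts as a deviation, can therefore differ between control and intervention.

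A post-allocation variable in the outcome model then causes two problems. If care-site changes affect disability, the model removes the part of the effect that runs through them. If severity drives both the change of site and the outcome, the participants who move, and those who do not, differ in severity between conditions, and an effect can appear where none exists. At stake is the reading of H3 for mRS, a secondary outcome. The H1 model in section 16.4.1 has no such term.

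**Working it through.** The protocol gives no effect size, transfer rate or deviation rate for H3, so there is no stated figure to reproduce. Every rate and coefficient below is an assumption. Two calculations show direction and range.

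**1. Selection through severity, with a true null.** Let U ~ N(0,1) be severity and A the condition.

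- logit P(transfer) = a_A + g·U, with a_A set to give the stated transfer rate in each condition
- logit P(mRS 0-2) = c − g·U, so condition has no effect
- g = 1.0 or 1.5

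Without the transfer term, the odds ratio (OR) for A is 1.00. With transfer in the model it becomes:

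| Transfers, control → intervention | g = 1.0 | g = 1.5 |
|---|---|---|
| unchanged | 1.00 | 1.00 |
| 40% → 30% | 0.93 | 0.88 |
| 40% → 20% | 0.86 | 0.77 |
| 30% → 40% | 1.07 | 1.14 |

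Simulation error is about 0.01. With U also in the model, the OR returns to about 1.00 in every row.

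**2. The stepped wedge with the term fitted as a random effect.** The simulation has 8 sites, 4 steps and 6 periods. A logistic mixed model is fitted with period and intervention as fixed effects and recruiting site as a random effect, with and without a random effect for deviation yes/no. Severity affects both transfer and outcome and is not in the model. Results are risk differences (RD) for mRS 0-2. The first pair of numbers in each row gives the assumed log-odds of intervention on transfer and of transfer on good outcome.

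| Scenario | True RD | Site only | Plus deviation term |
|---|---|---|---|
| Intervention does not alter transfer (0) | 0.099 | 0.101 | 0.099 |
| Small shift (−0.4, −0.5) | 0.113 | 0.114 | 0.098 |
| Strong shift, harmful transfer (−1.0, −1.0) | 0.138 | 0.139 | 0.083 |
| Same, no direct effect | 0.036 | 0.040 | −0.013 |
| True null, transfers lowered (−1.0, 0) | 0.000 | −0.001 | −0.020 |
| True null, transfers raised (+1.0, 0) | 0.000 | 0.000 | 0.023 |

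The loss is 0.113 − 0.098 = 0.015 under the small shift and 0.138 − 0.083 = 0.055 under the strong one. At 6 participants per site and period (8 × 6 × 6 = 288, near the planned 312), the strong shift gives 0.088 against a true 0.138, so shrinkage of the random effect does not remove the problem.

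**3. If the term means the final care site.** Under the strong shift, the RD is 0.140 against a true 0.138 when all sites exchange patients. When only regional patients move to metropolitan hospitals, it is 0.090 against a true 0.125. The second pattern is closer to the flow described in sections 5 and 8.

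**The case against.** Much can be said for the plan, and part of it stands.

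- **The bias is not certain.** With transfers unaffected by the package there is none. The package is staff training plus a coordinator one day a week, section 8 links transfers to early treatment, and no passage sets out to change them. Some may also precede recruitment. This stands: the bias is a possibility, not a demonstrated fact.
- **The clause covers deviations, not all transfers.** Section 11.1.2 has rules for transferred participants, so a transfer handled by those rules is not evidently a deviation. The 20% to 40% rates may overstate the exposure. This stands for size.
- **Severity adjustment would remove the null-case bias.** True in calculation 1, and severity is collected at baseline, but the H3 text does not include it. Adjustment would not restore an effect that runs through care-site changes.
- **The random effects may be crossed or multiple-membership.** This is a fair reading, and harmless under some transfer patterns but not under a one-way regional-to-metropolitan flow. It also means that an argument from a two-level factor being too small to estimate a variance cannot be made from this text.

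A reader might infer that H3 no longer compares participants as allocated, or that the clause breaks the intention-to-treat rule. The documents do not support that. Nothing reassigns site or condition, section 11.1.2 keeps a transferred control participant in the original site's control period, and section 16.4 states its rule for the primary analysis only.

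**Conclusion.** The point holds in a conditional form. As written, the H3 mRS model adjusts for something that follows allocation and that the package may alter, so it can fail to estimate the total effect of allocation. The distortion can go in either direction: in the scenarios tried it ran from nil, through 0.015 on the risk-difference scale for a small shift, to about 0.05 for a strong one, and an effect acting only through transfers changed sign. These sizes rest on assumed rates and severity effects, and the protocol gives nothing with which to choose among them. An unconditional statement that the mRS effect is biased would go too far. The matter is confined to one secondary outcome, but it is a stated analysis rule and worth changing.

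**What to change.** In section 16.4.2, delete the clause on care-site changes from the H3 model. Analyse mRS by recruiting site and its allocated phase, with a site random effect and period as a fixed effect as in the other secondary models. Include baseline type and severity of injury, as the occasions-of-service, carer-strain and HADS models already do. State in section 16.4 that the recruiting-site rule also covers the secondary outcomes.

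Report care-site changes and the resulting deviations by condition descriptively. If the influence of the later care site is of interest, fit a care-site or multiple-membership model with its random effects defined, labelled as supportive and not as the H3 result.

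The cost is a few sentences in the protocol or the SAP. No new data are needed, because recruiting site, phase and baseline severity are already recorded. In the simulations, the model without the term was within 0.007 of the true risk difference in every scenario.

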Secondary Outcome measures	
Clinical service provision (rehabilitation services provided),  Compliance with minimum process of care indicators at 12 and 26 weeks post injury,  Modified Rankin Scale at baseline, 12 and 26 weeks post injury,  Functional Independence Measure™ at baseline, 12 and 26 weeks post injury,  Hospital Anxiety Depression Scale at baseline, 12 and 26 weeks post injury,  Burden of care (Modified Caregiver Strain Index) at 12 and 26 weeks post injury,  Resource utilisation at 12 and 26 weeks post injury.
 
Process evaluation data
 
 
- Questionnaires measuring hospital staff satisfaction with cultural security training and attitude change following both completion of face to face and online training.
 
- Participant questionnaires measuring satisfaction with Aboriginal Brain Injury Coordinator service at 26 weeks.
 
- Interviews with a sub-section of participants (n=10) exploring participants' satisfaction with Aboriginal Brain Injury Coordinator service at 26 weeks
 
- Bi-annual Partner meetings incorporating feedback on the Aboriginal Brain Injury Coordinator service interviews with Aboriginal Brain Injury Coordinators at the completion of their contracts surrounding their experience of the role.
 

Study Design:	Stepped wedge cluster randomised controlled trial. Parallel process evaluation as per the TIDieR checklist.
Eligibility Criteria (Inclusion and Exclusion)	
Aboriginal participants with a newly documented brain injury to be identified, recruited, and first assessment completed within six weeks of onset.
 
Inclusion criteria:  Identification as Aboriginal (from medical file or through self-identification via personal communication with staff)  ≥Age 18 years

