### **10.3.5 Hospital Anxiety and Depression Scale**

The Hospital Anxiety and Depression Scale is a 14 item questionnaire designed to measure anxiety and depression in a general medical population and takes between 2-5 minutes to complete. There are seven items for anxiety and seven for depression and the two areas are scored separately. There is a 4 point scale for each. For both areas, scores that are less than 7 are considered ‘non-cases.’ Scores between 8-10 are considered mild, 11-14 = moderate, and 15-21 = severe.

The Hospital Anxiety and Depression Scale will be administered at baseline, 12 and 26 weeks post injury.

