**Scoring:**

Total score: Depression (D) \_\_\_\_\_ Anxiety (A) \_\_\_\_\_

0-7 = Normal

8-10 = Borderline abnormal (borderline case)

11-21 = Abnormal (case)

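### The H4 model does not say which HADS score is analysed and leaves out the scheduled baseline HADS

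*Protocol*

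**What the plan says.** Protocol 16.4.2 gives the HADS analysis for H4 a paragraph of its own. It sets a single longitudinal linear mixed model for anxiety and depression together and defines the response thus: "The outcome variable will be the Hospital Anxiety and Depression Scale at 12 and 26 weeks post brain injury". On adjustment it says "Type and severity of the brain injury will be controlled for in the model", then adds time period as a fixed effect and site as a random effect. No subscale is named, and the baseline HADS appears neither as a covariate nor as a modelled time point.

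H4, as worded in 16.1, predicts "less brain injury survivor anxiety and depression (Hospital Anxiety and Depression Scale) at 12 and 26 weeks post injury".

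On scoring, 10.3.5 says "There are seven items for anxiety and seven for depression and the two areas are scored separately". The HADS form in Appendix 1 has one total for depression and one for anxiety, with bands that run to 21, and no line for a combined total.

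On timing, 10.3.5 says "The Hospital Anxiety and Depression Scale will be administered at baseline, 12 and 26 weeks post injury". The Synopsis lists this secondary outcome as "Hospital Anxiety Depression Scale at baseline, 12 and 26 weeks post injury". Section 10.2.1, the table in 16.2 and the schedule in Appendix 1 also place the HADS at baseline.

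**The concern.** Two things in the H4 paragraph do not fit the rest of the protocol.

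First, it names one outcome variable where the instrument, as the protocol scores it, produces two. H4 makes a claim about anxiety and a claim about depression. An analyst working from 16.4.2 cannot tell which score enters the model, or whether one or two intervention effects will be reported.

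Second, 16.4.2 writes out the adjustment terms and the baseline value of the outcome is not among them. Participants are enrolled after their site's phase is set. Section 16.4.2 (Blinding) accepts that patients, most investigators and, in rural areas, assessors will probably know that phase. Only four pairs of sites are randomised (section 8), and the comparison runs partly across calendar time. People recruited in control and intervention phases may therefore differ in mood at entry, and injury type and severity need not capture that difference. Baseline HADS addresses it directly and would normally also reduce residual variance.

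At stake are the clarity and precision of a secondary result. The primary analysis is not affected.

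**Working it through.** **Step 1. What is modelled against what is measured.**

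| Item | H4 paragraph in 16.4.2 | Elsewhere in the protocol |
|---|---|---|
| Score | One outcome variable, the HADS | Two separate scores (10.3.5; form in Appendix 1); no combined total |
| Claim | One model | Less anxiety and less depression (H4 in 4.2 and 16.1) |
| Time points | 12 and 26 weeks | Baseline, 12 and 26 weeks (Synopsis, 10.2.1, 10.3.5, 16.2, Appendix 1) |
| Model terms | Injury type and severity, time period, site | Baseline HADS available but not listed |

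Two neighbouring passages help in reading this. The H3 model for the mRS in 16.4.2 does bring in the baseline measurement. The sentence in 16.4.1 on including differences in baseline characteristics belongs to the primary VAS model and is not repeated for H4. The HADS paragraph also has the same structure as the one before it on the Modified Caregiver Strain Index. That instrument has one total score and no baseline measurement, so the structure suits it and does not suit the HADS.

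**Step 2. Is there a planned figure to reproduce?** No. The protocol gives no HADS effect size, standard deviation, correlation or power. The sample size in 16.3 concerns the EQ-5D VAS only.

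**Step 3. Size of the possible gain from baseline adjustment.** Let r be the partial correlation between a baseline subscale score and the same subscale at follow-up, given injury type and severity. The between-participant residual variance is multiplied by 1 − r². The equivalent sample multiplier is 1/(1 − r²). The values of r are assumptions.

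| r (assumed) | 1 − r² | Reduction in variance | 1/(1 − r²) |
|---|---|---|---|
| 0.3 | 1 − 0.09 = 0.91 | 9% | 1.10 |
| 0.4 | 1 − 0.16 = 0.84 | 16% | 1.19 |
| 0.5 | 1 − 0.25 = 0.75 | 25% | 1.33 |
| 0.6 | 1 − 0.36 = 0.64 | 36% | 1.56 |

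These factors apply to the between-participant part of the error. Variation between sites and the cost of estimating period effects shrink less, so the gain in the precision of the intervention effect will be smaller than the table shows.

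**Step 4. Can baseline follow exposure?** Section 10.2.1 allows baseline up to 42 days after injury. The table in 16.2 (0 to 4 weeks) and Appendix 1 (Day 2 to Day 28) give shorter windows. In an intervention phase the participant may by then have been cared for by trained staff (11.1.1), and the coordinator may have visited in hospital (11.1.2). Baseline is preferably taken on the day of consent, and the coordinator sees enrolled participants, so the main route is earlier care by trained staff.

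**The case against.** The best defence has four parts.

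**The wording is shorthand.** Section 16.4.2 never speaks of a total or a sum. The protocol defines only two scores, so the instrument's name could stand for both. A reader might infer that the plan sums the subscales, and that opposite movements could then cancel. The document does not support that inference, and I do not rely on it. What stands is that one outcome variable is named and the score is not.

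**This is detail for the SAP.** If the subscale name were the only gap, that would be fair. But 16.4.2 itself writes down the outcome, its time points and the adjustment terms, and a SAP that follows it would carry the omission forward. It is also true that measuring the HADS at baseline does not promise adjustment for it, so this half is a choice that could be improved and not a contradiction.

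**Baseline may already carry some of the intervention.** This is the strongest point. Conditioning on a score taken after first exposure could remove part of an early effect, and an apparent imbalance could itself be an early effect. It limits the claim without defeating it: exposure before baseline is likely to be partial, and reporting both models shows how much depends on it.

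**Baseline is not simply discarded, nor certain to be complete.** The baseline characteristics in the H1 model (16.4.1) are unspecified and could include the HADS. The trial also enrols people with communication disorders and people who cannot consent for themselves (section 9), so a self-report scale may be missing for some. Both points stand: the baseline is scheduled for all, which does not mean it will be obtained from all.

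**Conclusion.** The point holds as a modest improvement to a secondary analysis. Section 16.4.2 leaves the analysed HADS score unstated for a hypothesis with two claims, and its listed terms omit a baseline value that is scheduled for all participants.

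The model without baseline is not invalid. It is less precise than it could be and leaves any phase difference in baseline mood unadjusted. A reader might go further and call the H4 estimate biased. The documents do not show that, because no imbalance is known and the unadjusted analysis avoids conditioning on a possibly post-exposure measure.

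The possible gain is about 9% to 36% lower between-participant residual variance, or 1.10 to 1.56 times the effective sample. It rests entirely on the assumed partial correlation of 0.3 to 0.6 and is an upper guide once clustering and period effects are counted.

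**What to change.** In 16.4.2, replace the single HADS model by two, one for HADS-Anxiety and one for HADS-Depression, each at 12 and 26 weeks. Keep injury type and severity, time period and site as planned. Add the matching baseline subscale score and the time from injury to baseline as covariates. State a simple rule for missing baseline scores, and say how the two results will be read together against H4.

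Also report each model without the baseline score, because baseline may follow care by trained staff or coordinator contact in intervention phases.

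No new data are needed. The costs are a short amendment, a missing-covariate rule, one more outcome to interpret, and a second version of each model whose difference from the first must be explained.
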